9.1.2. Secondary Endpoints

- Average weight, average length, and average head circumference of the children from birth to 48 months
- Number and proportion of abnormalities diagnosed during pediatric check-ups under statutory programs in Germany and reported in the standardized German pediatric check-up booklet “Kinderuntersuchungsheft” (data on check-ups 1-8 will be collected covering the first 46 - 48 months of life). Refer to Annex 3 for recommended timepoints and details on the examinations.
- Number and proportion of women discontinuing SC Peginterferon beta-1a or IM Interferon beta-1a therapy during pregnancy and time to discontinuation in relation to beginning of pregnancy

CONFIDENTIAL

The information contained herein may not be used, disclosed, or published without the written consent of Biogen MA Inc.

- Number and proportion of women starting SC Peginterferon beta-1a or IM Interferon beta-1a therapy during pregnancy and time to start in relation to beginning of pregnancy
- Number and proportion of women restarting SC Peginterferon beta-1a or IM Interferon beta-1a therapy after birth and time to restart in relation to birth
- Number and proportion of women starting another MS therapy during/after pregnancy and time to start in relation to birth
- Number and proportion of women using other therapies during pregnancy (categorized by Paracetamol, other therapies for the alleviation of FLS), folic acid, medication for depression, corticosteroids, adrenocorticotrophic hormone, other therapies)
- Number and proportion of MS relapses in women with SC Peginterferon beta-1a or IM Interferon beta-1a therapy before, during and after pregnancy
- Change of EDSS during and after pregnancy to EDSS before pregnancy
- Lactation: number of women breastfeeding under SC Peginterferon beta-1a or IM Interferon beta-1a therapy and duration of SC Peginterferon beta-1a or IM Interferon beta-1a exposed breastfeeding
- Time to first MS relapse after introduction of the first supplemental feedings in women with SC Peginterferon beta-1a or IM Interferon beta-1a therapy during lactation

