9.2.3. Overall Study Duration and Follow-Up

9.2.3.1. Enrollment

The study period will start with the identification and enrollment of patients meeting the eligibility criteria. Recruitment is planned for 3 months. The end of study is defined as end of overall data collection when the database for analysis is completely available.

The Sponsor may terminate or prolong this study at any time, after informing the participating parties.

Data of the retrospective study part will be extracted from the German MS Service-Center database on the basis of the PSP registration form, i.e. the signed privacy policy. No separate patient information and consent procedure is planned for this part.

The study participation in the prospective study part starts with signature of the ICF and ends with the completion of the patient questionnaire. As the provision of the ICF by the MSSC and the return of the signed ICF by the patient is done by mail, both actions are expected to take 1-2 weeks. The telephone interview will take place only after having obtained the signed ICF. Depending on the availability of the patient for the telephone interview, another week has to be calculated resulting in an average study duration of about 2-3 weeks per patient in the prospective study part.

Patients in the prospective study part are informed that they have the right to withdraw from the study at any time, without prejudice to their medical care, and that they are not obliged to state their reasons. Any withdrawal must be fully documented in the MSSC data base. Withdrawn patients are not followed-up.

Unique identification numbers will be assigned to all pregnancy reports of participants enrolled in the study to track them throughout the study. In case of multiple pregnancies, separate identification numbers will be assigned for the pregnancies. Any identification

CONFIDENTIAL

The information contained herein may not be used, disclosed, or published without the written consent of Biogen MA Inc.

numbers that are assigned will not be reused even if a participant withdraws from the study prematurely.

An individual study participant may be included only once in the study – however, data of multiple pregnancies will be collected separately.

Participants who prematurely withdraw from the study for any reason will not be eligible to re-enroll.

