9.4.2. Prospective Data Capture

If the pregnancy report or the pregnancy outcome report is incomplete, i.e. the data above was not collected, the open questions will be addressed during a telephone interview performed by the MSSC and the new information will be entered into the MSSC database. No further assessments other than completion of the questionnaire are applicable for patients participating in the prospective study part. The patient questionnaire is completed at a single point of time during the telephone interview performed by the MSSC.

The patient questionnaire covers the following questions:

- Abnormalities diagnosed during pediatric check-ups under statutory programs as reported in the standardized German pediatric check-up booklet “Kinderuntersuchungsheft” (data on check-ups 1-8 will be collected covering the first 46-48 months of life)
- Pregnancy and family anamnesis
- Vitamin K prophylaxis
- Body weight, height, head circumference of the child as documented for check-ups 2-8.
- Lactation:
 - Exclusive breastfeeding and duration (1st week, 1 month, 2 months, 3 months, 5 months, 6 months, 7-9 months, 10-12 months, > 12 months) of breastfeeding
 - Supplemental feedings (starting month after birth)
- Other MS therapies (non-interferon beta-1a DMTs) during or after pregnancy and start relative to birth (during pregnancy, < 1 week after birth, after 1 week, after 2 weeks, after 3 weeks, after 4 weeks, after 6 weeks, after 2 months, after 3 months, after 4 months, after 5 months, after 6 months, after 7 months, after 8 months, after 9 months, after 10 months, after 1 months, after 12 months or later))
- Frequency of MS relapses in the year before pregnancy
- Time (1st trimester, 2nd trimester, 3rd trimester) and frequency of MS relapses during pregnancy

CONFIDENTIAL

The information contained herein may not be used, disclosed, or published without the written consent of Biogen MA Inc.

- Time (< 1st month, 1st – 2nd month, 3rd - 4th month, 5th - 6th month, 7th - 8th month, 9th - 10th month, 11th - 12th month, 13th - 14th month, 15th - 16th month, 17th - 18th month, > 18th months) and frequency of MS relapses after pregnancy/birth
- EDSS before, during and after pregnancy

The information collected by the MSSC will be stored in a secure database.

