9.5. Study Size

Since this is an exploratory study and no formal hypothesis-testing will be carried out, there is no formal sample size calculation. The sample size of this study depends on how many patients are eligible to participate in this observation and will agree to provide data for the questionnaire.

As of mid-July 2020, there were n = 202 pregnancy and pregnancy outcome reports for 184 female patients under SC Peginterferon beta-1a and n = 245 pregnancy and pregnancy outcome reports for 199 female patients treated with IM Interferon beta-1a in the MSSC database. The outcome of 368 pregnancies was a live birth, hence qualify for the prospective study part. About 290 patient questionnaires are expected to be completed during the telephone interview (80% return rate estimated). This number might increase until 15th October 2020 - the cut-off point for data collection.

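### The post-birth relapse period does not close at the next conception, so in a woman with two recorded live births one relapse can be counted in more than one period

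*Protocol*

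**What the plan says.** Section 9.1.2 lists as a secondary endpoint "Number and proportion of MS relapses in women with SC Peginterferon beta-1a or IM Interferon beta-1a therapy before, during and after pregnancy". Section 9.4.2 says how the relapses are captured, at one telephone interview:

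- before: "Frequency of MS relapses in the year before pregnancy";
- during: "Time (1st trimester, 2nd trimester, 3rd trimester) and frequency of MS relapses during pregnancy";
- after: ten bounded bands up to month 18, then a last band without an upper limit, "> 18th months) and frequency of MS relapses after pregnancy/birth".

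On repeat pregnancies, section 9.2.3.1 states: "An individual study participant may be included only once in the study – however, data of multiple pregnancies will be collected separately". It adds: "In case of multiple pregnancies, separate identification numbers will be assigned for the pregnancies". Section 9.7 makes the number of pregnancies in the group the default denominator for percentages.

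Section 9.5 shows that repeat pregnancies are present: "n = 202 pregnancy and pregnancy outcome reports for 184 female patients" for the SC product, and 245 reports for 199 women for the IM product.

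No section ends the post-birth period at a later conception, assigns a relapse to a single period, or limits the relapse endpoint to one pregnancy per woman.

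**The concern.** The endpoint sets relapses before, during and after pregnancy beside each other, and the three periods should not share events. For a woman with one recorded pregnancy they do not. For a woman with two, the post-birth period of the first runs on through the second.

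This has three consequences:

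- One relapse can appear on both sides of the comparison, and the column totals can exceed the relapses that occurred.
- The post-birth period can contain a later pregnancy. Section 7 cites evidence that relapse rates fall in pregnancy and resume after birth, so the mixture blurs the pattern the endpoint is meant to show.
- Section 9.7.2 splits the secondary endpoints by treatment pattern around each pregnancy. If a woman continued treatment in one pregnancy and stopped in the next, the same relapse can enter two exposure subgroups.

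**Working it through.** **1. Unit of the questionnaire.** Section 9.5 gives 368 live-birth pregnancies, an 80% return rate and about 290 questionnaires.

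- Per pregnancy: 0.80 × 368 = 294.4, which agrees with about 290.
- Per woman, scaling by women over reports: 368 × 383/447 = 315.3, and 0.80 × 315.3 = 252.2, which does not agree.

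The protocol's own figure therefore treats the pregnancy as the unit, in line with sections 9.2.3.1 and 9.7.

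**2. Repeat pregnancies.**

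- Reports: 202 + 245 = 447.
- Women: at most 184 + 199 = 383, since a woman could appear under both products.
- Repeat reports: at least 447 − 383 = 64 (18 SC, 46 IM), or 64/447 = 14.3%, if no report is duplicated.

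**3. Questionnaires affected.** This assumes the same repeat share among live births and one 80% response covering both pregnancies of a woman.

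- Live-birth fraction applied once: 64 × 368/447 × 0.80 = 42.2. (The same share of the stated 290 is 290 × 64/447 = 41.5.)
- Both pregnancies must be live births, with independent outcomes: 64 × (368/447)² × 0.80 = 34.7.

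The result is roughly 35 to 42.

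**4. Overlap per pair.** Let *g* be the months from the first birth to the second conception, and *T* the months from the second birth to the interview. Take a pregnancy as 9 months. The part of the first pregnancy's post-birth period that is also counted for the second is

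min(12, *g*) + 9 + *T* months.

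The terms are the year before, the second pregnancy and the time after it. If *g* is under 12, the year before also reaches 12 − *g* months back into the first pregnancy (9 at most), which this formula leaves out.

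**5. Relapses counted twice.** Pairs × overlap/12 × annual relapse rate, with 41.5 pairs. The values of *g*, *T* and the rate are assumptions; the protocol gives none of them.

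| *g* | *T* | Overlap (months) | Rate 0.1 | Rate 0.3 | Rate 0.5 |
|---|---|---|---|---|---|
| 6 | 6 | 21 | 7.3 | 21.8 | 36.3 |
| 12 | 24 | 45 | 15.6 | 46.7 | 77.9 |
| 24 | 36 | 57 | 19.7 | 59.2 | 98.6 |

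The range is about 7 to 99. With 34.7 pairs the ends become 34.7 × 21/12 × 0.1 = 6 and 34.7 × 57/12 × 0.5 = 82.

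**6. What a change of window removes.**

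- Ending the post-birth period at the next conception removes the overlap with the second pregnancy and the time after it. It leaves min(12, *g*) months shared with the year before.
- A cap at month 18 alone leaves 18 − max(0, *g* − 12) months: 18 for gaps of 6 or 12 months, 6 for a gap of 24.

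Neither step is sufficient alone, so the remaining overlap has to be shown separately.

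**The case against.** The strongest reply is that this is detail for the statistical analysis plan. Section 9.7 promises such a plan, and rules for repeat pregnancies and period assignment are ordinary content for it. That stands for tabulation but not for capture. Relapses are recorded in bands rather than by date, at one interview after which participation ends. An entry in the open band cannot later be placed before or after a next conception from that entry alone.

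Second, only the eleventh band is open, and nothing says that all bands will be summed into one post-birth count. This is fair, and a plan that reported the open band separately would remove part of the problem. It would not remove all of it, because a second conception within 18 months puts the overlap inside the bounded bands.

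Third, with the pregnancy as unit, a relapse can properly be post-birth for one pregnancy and pre-conception for the next, and the study is descriptive and non-comparative (sections 9.7 and 9.9). This lowers the weight. Sections 8.1 and 8.3 nevertheless speak of differences in progression and of effects on disease activity, which a reader will take from these tables.

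Fourth, the questionnaire itself is not shown and may tell interviewers how to treat a later pregnancy. That is possible, but the protocol does not say so.

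One tempting reply fails: being included only once does not prevent the overlap, because the same sentence continues "data of multiple pregnancies will be collected separately".

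**Conclusion.** The point holds as a defect in how the relapse periods are defined. The mechanism follows from sections 9.2.3.1, 9.4.2 and 9.7 as written. It arises only where both pregnancies are in the questionnaire set. A relapse between the two births but more than 12 months before the second conception is counted once.

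The size is less certain. At least 64 of 447 reports (14.3%) are repeats, if no report is duplicated. The 35 to 42 affected questionnaires rest on an assumed equal repeat share and 80% response. The 7 to 99 relapses counted twice rest on assumed rates, gaps and follow-up.

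Two stronger readings are not supported.

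- A reader might infer that about a fifth of post-birth relapses is counted twice. With 42 pairs, 0.5 relapses a year outside and 0.2 in pregnancy, an 18-month gap and 24 or 36 months after the last birth, one obtains 69 of 332 (21%) or 90 of 479 (19%). Every rate, gap and follow-up time in that figure is assumed, so it is one scenario within the range.
- A reader might infer that the disease-activity objective fails as a whole. It does not rest on these counts alone, since section 9.1.2 also lists EDSS change and time to first relapse after supplemental feeding.

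The definition should be corrected before interviews begin, because the bands cannot be separated afterwards.

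**What to change.** In sections 9.1.2, 9.4.2 and 9.7:

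1. End each pregnancy's post-birth relapse window at the earliest of the next conception, a fixed month at an existing band edge (for example month 12 or 18) and the interview. State how the band in which the next conception falls is assigned.
2. Report relapses in the open last band separately, outside the before/during/after comparison.
3. Show separately, rather than exclude, pregnancies whose year before overlaps an earlier pregnancy or its post-birth window. Excluding them would select the sample by spacing of pregnancies.
4. Add the same table restricted to each woman's first recorded pregnancy, and carry a woman-level key into the analysis file. Section 9.2.3.1 describes identifiers only per pregnancy, while the counts in section 9.5 imply that women can be identified in the source database.

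The cost is some wording, one extra table and one key variable. Late relapses leave the main comparison but stay in the listings. Month 12 would drop the bands for months 13 to 18 from that comparison and month 18 would keep them; either is workable with the planned questionnaire.

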9.5. Study Size

Since this is an exploratory study and no formal hypothesis-testing will be carried out, there is no formal sample size calculation. The sample size of this study depends on how many patients are eligible to participate in this observation and will agree to provide data for the questionnaire.

As of mid-July 2020, there were n = 202 pregnancy and pregnancy outcome reports for 184 female patients under SC Peginterferon beta-1a and n = 245 pregnancy and pregnancy outcome reports for 199 female patients treated with IM Interferon beta-1a in the MSSC database. The outcome of 368 pregnancies was a live birth, hence qualify for the prospective study part. About 290 patient questionnaires are expected to be completed during the telephone interview (80% return rate estimated). This number might increase until 15th October 2020 - the cut-off point for data collection.

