
Study Design:
	
This non-interventional, voluntary PASS is designed as a single-center open-label survey.
 
Spontaneously reported safety data are available for pregnant MS patients treated with SC interferon beta therapy or an IM interferon beta therapy in the German PSP of the MSSC.
 
In addition, a prospective data collection is performed by completing a standardized paper questionnaire while interviewing MS patients who reported a “live birth” and for which a signed ICF is available.

Population:
	
All female patients treated with SC Peginterferon beta-1a therapy or IM Interferon beta-1a therapy who fulfill the inclusion criteria are eligible to participate in the study.
 
Inclusion Criteria
 
 1. Female patients of at least 18 years at time of informed consent 2. Diagnosed RRMS or CIS (CIS indication only applicable for interferon beta-1a) 3. Exposure to either SC Peginterferon beta-1a therapy or IM Interferon beta-1a therapy before or during pregnancy 4. Registered in the PSP of the MSSC and agreed in writing to the privacy policy of the registration form 5. Reported pregnancy data (pregnancy report and pregnancy outcome report) available at MSSC. Note: only pregnancy data (i.e. obtained until 15 October 2020) will be considered. 
For the prospective part of the study:
 
 6. Ability to understand the purpose of the study and provide signed and dated study-specific informed consent form (ICF) 7. Pregnancy outcome in the retrospectively collected data was a live birth

Variables:
	
 • Demographic data • SC Peginterferon beta-1a or IM Interferon beta-1a use, including treatment duration, prior to, during and after pregnancy • Concomitant medication prior to and during pregnancy • Pregnancy outcome, including gestation week and description of abnormalities of the fetus, reason for termination, diagnostics, etc. • Complications during pregnancy • Type of delivery, complications during delivery or reasons for an intervention • Placenta normal/abnormal

CONFIDENTIAL

The information contained herein may not be used, disclosed, or published without the written consent of Biogen MA Inc.

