Peginterferon beta-1a, pegylated interferon beta-1a, was developed as a modern pegylated version of the native protein interferon beta-1a with improved pharmacological properties to provide an interferon with increased interferon efficacy, higher interferon exposure, decreased renal clearance and longer elimination half-life to facilitate adherence by reducing frequency of application. It was approved by the EMA in July 2014 and has been available in Germany since September 2014. Peginterferon beta-1a is injected every 2 weeks. Peginterferon beta-1a hence constitutes an additional option for injectable disease-modifying therapy of RRMS with an established risk-benefit ratio [Calabresi 2014; Arnold 2014; Kieseier 2015; Arnold 2017; Calabresi 2017; Arnold 2018; Newsome 2018], established injectable efficacy [Calabresi 2014; Arnold 2014; Kieseier 2015; Arnold 2017; Calabresi 2017; Arnold 2018; Newsome 2018] and statistically significant lowest total cumulative flu-like symptoms (FLS) duration under the interferons [Hendin 2018]. This might be especially useful in the sensitive period of pregnancy and lactation.

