9.1.1. Primary Endpoints

- Number and proportion of
 - live births without congenital anomalies,
 - live births with congenital anomalies,
 - ectopic pregnancies,
 - spontaneous abortions,
 - elective abortions,
 - preterm births,
 - stillbirths

A spontaneous abortion is defined as fetal death before 22 weeks of gestation. A still birth is defined as fetal death at > 22 weeks gestation. A preterm birth is a birth before 37 completed weeks of gestation.

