9.2.1. Selection Criteria

The patients will only be included in the study if they meet all of the following criteria:

Inclusion Criteria

1. Female patients of at least 18 years at time of informed consent
2. Diagnosed RRMS or CIS (CIS indication only applicable for interferon beta-1a)

CONFIDENTIAL

The information contained herein may not be used, disclosed, or published without the written consent of
Biogen MA Inc.

3. Exposure to either SC Peginterferon beta-1a therapy or an IM Interferon beta-1a therapy before or during pregnancy
4. Registered in the PSP of the MSSC and agreed in writing to the privacy policy of the registration form
5. Reported pregnancy data (pregnancy report and pregnancy outcome report) available at MSSC. Note: only pregnancy data (i.e. obtained until 15 October 2021) will be considered.

For the prospective part of the study:

6. Ability to understand the purpose of the study and provide signed and dated study-specific informed consent form (ICF)
7. Pregnancy outcome in the retrospectively collected data was a live birth

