9.6. Data Management

MS Service-Center database:

The Biogen MS Service-Center provides medical information to German MS patients on request. Furthermore, it offers enrollment to a patient support program for SC Peginterferon beta-1a and IM Interferon beta-1a patients including injection handling training and individual adherence coaching from a personal coach upon medical need. Services have been provided since October 2014 from Audimedes GmbH, certified according to ISO 9001:2015 criteria. Compliance with these criteria is audited annually by an external certified audit organization. Database includes data of about 45,000 patients with MS.

From 2014 until December 2019 3, 615 patients under IM Interferon beta-1a treatment and 7,529 patients under SC Peginterferon beta-1a treatment have been enrolled to the patient support program. In the database, demographics and therapeutic history including adverse events, product complaints and pregnancy reports are captured in real time. All personnel dealing with the patient information and database undergo regular training to ensure quality of information, communication skills and quality of data in the database. All data is pseudonymized and pooled for this analysis.

Study database:

Data collection for the retrospective study part will be performed by extracting the relevant data from the existing MSSC database and importing it into an electronic PDF (ePDF) by a CRO. During the telephone interview, missing data will be completed directly in the ePDF, if appropriate. After the CRO has received all completed ePDFs, all

CONFIDENTIAL

The information contained herein may not be used, disclosed, or published without the written consent of
Biogen MA Inc.

data will be exported and used for analysis by the CRO as well as for updating the MSSC database (Audimedex GmbH).

All relevant data for the prospective study part is documented on standardized patient questionnaires provided as ePDF. The MSSC personnel documents the results of the telephone interview directly in the ePDF and after completion, the ePDF is transferred to the CRO to export and analyze the data together with the retrospective data.

Personal data of patients are gathered, stored and processed exclusively in a pseudonymous form according to national data protection laws.

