9.7.1. Analysis Population

9.7.1.1. Primary Endpoint Analysis

The analysis set for the primary objective will be defined by the group of patients that are registered in the PSP, agreed to the privacy policy of the registration form, and were

CONFIDENTIAL

The information contained herein may not be used, disclosed, or published without the written consent of
Biogen MA Inc.

eligible to participate in this observation (see 9.2.1 **Fehler! Verweisquelle konnte nicht gefunden werden.**).

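### The primary set is closed by a calendar cut-off on outcome reports with no limit on when the pregnancy began, so recent pregnancies enter mainly if they ended early; taken alone this adds about 1 point to a 10.7% loss proportion.

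*Protocol*

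**What the plan says.** Criterion 5 in section 9.2.1 requires "Reported pregnancy data (pregnancy report and pregnancy outcome report) available at MSSC". Section 9.4.1 says that the outcome report is completed only once the pregnancy is over, so an ongoing pregnancy cannot qualify.

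The calendar limit applies to when the data were obtained, and it is given in two versions:
- Abstract, criterion 5: "Note: only pregnancy data (i.e. obtained until 15 October 2020) will be considered"
- Section 9.2.1, criterion 5: "Note: only pregnancy data (i.e. obtained until 15 October 2021) will be considered"
- Section 9.5 agrees with the Abstract: "This number might increase until 15th October 2020 - the cut-off point for data collection". That sentence follows the questionnaire count, so criterion 5 is the governing text for the primary set.

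Section 9.7.1.1 adds no limit on the start of pregnancy: "The analysis set for the primary objective will be defined by the group of patients that are registered in the PSP", with privacy consent and eligibility under 9.2.1. Section 9.7 takes all pregnancies in the group as the denominator. Section 9.1.1 makes the primary endpoints the proportions of live births with and without anomalies, ectopic pregnancies, spontaneous and elective abortions, preterm births and stillbirths. It also fixes the term boundary: "A preterm birth is a birth before 37 completed weeks of gestation".

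The limitations in 9.9 name the missing comparator and missing or implausible values, but not this selection. The checklist in Annex 2 marks selection bias as not applicable in its Section 7, yet in its Section 12 says that 9.9 discusses it.

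**The concern.** The primary outcomes occur at very different gestational ages, but all must be known by one calendar date. Take two pregnancies that begin in March 2020 under a cut-off of 15 October 2020. One miscarries in May and is counted. The other is healthy in October and does not appear at all. This happens even with complete and immediate reporting, so better follow-up does not cure it.

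Taken alone, the mechanism raises the proportions of early-ending outcomes and lowers the live-birth proportion. The study has no internal reference group, so its percentages can be read only against outside figures, such as the spontaneous-abortion prevalence in section 7.1.2 (10.7% in the European registry, up to 21% in the general population). A systematic shift does not shrink as pregnancies are added.

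**Working it through.** **The plan's own figures.** The protocol gives no figure for the cut-off effect. Section 9.5 reports 202 + 245 = 447 pregnancies with outcome reports at mid-July 2020, of which 368 were live births: 368/447 = 82.3%, leaving 79 (17.7%) with any other outcome. Its questionnaire estimate reproduces: 0.80 × 368 = 294, against about 290 stated.

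**Who can enter.** With a cut-off of 15 October 2020:
- Begun after 30 January 2020 (less than 37 weeks before): no term birth is possible.
- Begun 37 to 42 weeks before: a term birth can enter only if it comes early enough, so term births are under-represented.
- Begun on or before 26 December 2019 (42 weeks or more): all outcomes can have occurred.

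**Size.** Inputs:
- Window: W = 315 weeks, from 1 October 2014 to 15 October 2020. The start is an assumption taken from 9.6: "Services have been provided since October 2014 from Audimedes GmbH".
- Loss proportion: p = 10.7% (section 7.1.2).
- Assumptions not in the protocol: losses at week gL = 9 or 10, births at week gB = 39, starts spread evenly, no pregnancies already under way at programme start, reporting lag r = 0 or 8 weeks.

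A pregnancy ending at week g is included only if it began at least g + r weeks before the cut-off, so

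observed loss share = p(W − gL − r) / [p(W − gL − r) + (1 − p)(W − gB − r)].

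With gL = 10 and r = 0: 0.107 × 305.1 = 32.65; 0.893 × 276.1 = 246.6; share = 32.65/279.2 = **11.7%**, a shift of +1.0 point.

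| Scenario | 10.7% is observed as |
|---|---|
| Even starts, gL 9 or 10, r = 0 | 11.7% |
| Even starts, r = 8 weeks | 11.7% (under 0.1 point more) |
| Cut-off 15 October 2021 (W = 367) | 11.5% |
| IM part fully offset: (202 × 11.7% + 245 × 10.7%)/447 | about 11.2% |
| Starts growing 20% a year | 12.4% |
| Starts growing linearly from zero | 12.8% |

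The offset row reflects IM pregnancies already under way when the programme began, which would add births at the early end. The same cannot apply to peginterferon to any extent: "It was approved by the EMA in July 2014 and has been available in Germany since September 2014". The growth rows are illustrative, because section 9.6 gives enrolment totals but no time course.

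**Against sampling error.** 95% half-width for 10.7% of 447: 1.96 × √(0.107 × 0.893/447) = 2.9 points.

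**Effect of a start-date limit.** The model gives 447/279.2 = 1.60 pregnancy starts a week. Restricting to starts at least 42 weeks before the cut-off leaves 1.60 × 273.1 = 437 of 447 and returns 10.7% when there is no lag. If reports in fact arrive 13 weeks after the event, a bare 42-week limit still gives 0.107 × 273.1/(0.107 × 273.1 + 0.893 × 263.1) = 11.1%. The limit therefore needs a lag allowance.

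**The case against.** The strongest case against is that the effect is small and its net direction unknown. One point on 10.7% is about a third of the sampling half-width, in a descriptive study without tests. IM pregnancies are 245 of 447 and can offset it at the start of the window. Early losses that are never reported pull the other way. The protocol gives no start or report dates to settle the balance. All of this stands, and it limits the claim to this mechanism taken alone.

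A reader might infer more than the documents support:
- That nothing begun in the last 40 weeks can be a term birth. Under 9.1.1 a birth at 37 completed weeks is not preterm, so the strict statement covers 37 weeks.
- That a true 21% would be shown as about 23%. At mid-July 2020 all outcomes other than live birth were at most 17.7%, and that share already includes any cut-off effect.
- That pregnancies begun after the September 2019 label change would show a much larger distortion and make continued use look harmful. The subgroups in 9.7.2 follow treatment history, not calendar period, so no such analysis is planned.

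It can also be said that a restricted set belongs in the statistical analysis plan. That stands only for details such as the lag allowance: the selection itself is fixed by the protocol's eligibility rule and primary set.

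**Conclusion.** The point holds in limited form. Criterion 5 and the primary analysis set over-represent early-ending outcomes among recent pregnancies, and 9.9 does not say so. Taken alone, the mechanism moves a true 10.7% to about 11.7% with even starts from October 2014, about 11.2% with full IM offset, and 12% to 13% if pregnancies grew over time, which the protocol does not show. It would be wrong to conclude that the reported loss proportions will be too high on balance. The case for acting is that this component is systematic, can be removed by definition, and affects primary results that have only outside figures for comparison. The conflicting cut-off dates change the size little (11.5% with 2021), but they decide which pregnancies are in the set. The 2021 date also lies after the planned end of data collection (31 March 2021) and final report (30 June 2021).

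**What to change.** 1. Reconcile the cut-off date between the Abstract, 9.2.1 and 9.5.
2. In 9.7.1.1 only, state that the primary proportions use pregnancies whose start (last menstrual period, or outcome date minus gestation week) lies at least 42 weeks plus a stated reporting-lag allowance before the cut-off, whatever their outcome. For the 2020 date this is 26 December 2019 minus the allowance. Leave criterion 5 unchanged: it governs both study parts, and a limit there could remove live births from the prospective part.
3. List later pregnancies by outcome and show the unrestricted proportions as a sensitivity analysis.
4. Report separately the pregnancies already under way at registration or programme start.
5. Name this selection in 9.9.

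**Cost.** A few sentences and one or two tables. Under the model, 42 weeks moves about 1.60 × 0.107 × 32 = 5.5 losses out of the primary table, or about 9 if the share of all other outcomes (17.7%) is used, so roughly 5 to 10, plus a few other early-ending pregnancies and about 4 births. Each further week of lag allowance costs about 1.6 pregnancies. Section 9.4.1 lists gestation week but neither last menstrual period nor outcome date. The primary subgroups in 9.7.2 already need treatment placed relative to the start of pregnancy, so start dates should largely be derivable. Pregnancies where they are not must be counted and shown.
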